# 9 STATISTICAL CONSIDERATIONS

#### 9.1 Sample size

The sample size for this trial will be adaptively determined through a phase 2/3 design. Enrollment is planned to last approximately 2 months. Each patient will be randomly allocated to Reparixin or Control according to a randomization ratio of 2:1 and he/she will be followed for the entire treatment and follow-up duration for collecting the efficacy endpoints of each study phase.

For the Phase 2 portion of the study, the primary analysis will compare Reparixin versus Control in terms of time to a composite endpoint (primary endpoint of phase 2) including the following events: requirement of supplemental oxygen treatment, mechanical ventilation use, admission to ICU, and any requirement of rescue medication. Based on clinical experience, an improvement of the median time freedom from composite event of 1.5 times is expected. Assuming an exponential distribution, a total sample size of 48 patients will allow to provide 80% power to show superiority of Reparixin compared to control using a log-rank test at a one-sided significance level of 0.025.

The sample size for the phase 3 is based on assessment of superiority of Reparixin compared to control arm in terms of freedom from a composite endpoint (primary endpoint of phase 3) of severe events including death, admission to the ICU, requirement of mechanical ventilation.

Based on same assumptions of phase 2 regarding randomization (2:1) and expecting to double the median time freedom from severe composite event using Reparixin compared to control (from 2-4 to 4-8 days), a total sample size of 111 patients will allow to achieve a power of 90% to show superiority of Reparixin over control using a log-rank test at a one-sided significance level of 0.025. No drop-out are expected to happen. The number of patients to be included may be revised based on considerations from Phase 2 data analysis.

Primary endpoint of phase 3 will be tested only if superiority of Reparixin is shown in phase 2. Thus, the overall type I error of the study will be controlled at 0.025 via the hierarchical testing procedure.

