4.1 General

Appropriate descriptive statistics will be produced, according to the variable:

- for continuous data n , mean, standard deviation (SD), median, Q1-Q3, and range (minimum and maximum) will be presented;
- for categorical data, frequency distributions and percentages will be presented;
- for time-to-event variables, cumulative freedom from event will be evaluated using Kaplan-Meier (KM) method. The degree of uncertainty will be expressed with 95% confidence limits (calculated per the method proposed by Greenwood³). Comparison of curves among arms will be performed with the log-rank test. KM graphs will be presented along with the number of subject-at-risk at exact time points. Subjects who have discontinued/terminated the study without an event will be censored at the date of study discontinuation/termination. Subjects ongoing and who are free from event at the time of database lock (for example at interim analyses) will be censored at the last available date.

Unless otherwise specified, hypothesis testing will be carried out at the $\alpha = 0.050$ level (two-sided) when comparing treatments. For all inferential analyses, p-value will be rounded to three decimal places. Statistical significance will be declared if the rounded p-value will be less than or equal to 0.050. For primary analysis only (section 7.1.2), p-values will be provided at 5th decimal place, in order to compare with efficacy and futility thresholds specified in section 4.5.

Additional post-hoc analysis may be produced to further allow comparison between reparixin and control, according to the results obtained. Any unplanned analyses as well as deviations from the original statistical plan will be clearly documented in the Clinical Study Report.

Derivation rules for efficacy and safety analyses are reported in Table 7 in section 9.

All the data collected and derived in the study will be presented in subject data listings by centre.

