7.1.2 Analysis details

The composite endpoints for phase 2 and phase 3 (section 3.5.1) will be summarized along with their single component by a binomial response rate at each time point (only the first event will be considered). The Clopper-Pearson method will be used to estimate the two-sided 95% CIs.

Primary analyses on time to composite endpoint(s) will be performed using the KM methodology and the one-

sided log-rank test will be used to test for differences between treatment groups. See section 4.1 for more details on time-to-event analysis and representation.

The primary endpoint of phase 2 will be assessed also in phase 3 as secondary analysis, and vice versa.

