7.1.3 Sensitivity analysis

7.1.3.1 Phase 2

Results of primary analysis will be assessed in sensitivity analyses as detailed below.

- The comparison between treatment and control will be performed by means of a Cox regression model, using age class, gender and clinical severity score at baseline as covariates, to assess the robustness of results on primary endpoint versus the presence of confounding factors. Additional covariates might be included after DRM in case relevant baseline imbalance will be identified between groups, despite randomization. The assumptions of proportionality will be investigated with a time-dependent exploratory variable, which is defined as $\text{treatment} * \{\log[\text{time to event}]\}$. If the p-value from the Wald Chi-squared statistic for this variable is less than 5% there is evidence of a departure from the adjusted model assumptions. In case of non-proportional hazards, a Weibull model will be assumed as parametric form of the distribution of survival times. The treatment group will be included in the model as covariate.
- Time to event for each single component of the primary endpoint will be performed separately in order to adjust for the presence of possible competing risks. The following events:
 - first supplemental oxygen requirement,
 - first mechanical ventilation use,
 - first admission to ICU, and
 - first use of a rescue medication for any reason

will be analyzed according to survival analysis methodology detailed in section 4.1 with the following modifications:

- the common representation of survival curves using the Kaplan-Meier estimator will be replaced by the cumulative incidence function,
- the presence of other competing event(s) is/are treated as censored.
- A modified composite endpoint of phase 2 will be analyzed adding “death” as fifth component. It will be analyzed according to section 7.1.2 to assess the robustness of results on primary endpoint versus the presence of censoring due to fatal events.

Decision to proceed/not proceed to phase 3 will be based only on primary analysis results, despite inconsistencies with sensitivity analyses. Sensitivity results will be interpreted and discussed in the clinical study report and will be used to eventually adjust adaptations for the phase 3.

7.1.3.2 Phase 3

Results of primary analysis will be assessed in sensitivity analyses as detailed below.

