- The comparison between treatment and control will be performed by means of a regression model, using the same method (Cox or Weibull model) and covariates identified during phase 2, to assess the robustness of results on primary endpoint versus the presence of confounding factors.
- Time to event for each single component of the severe primary endpoint will be performed separately in order to adjust for the presence of possible competing risks. The following events:
 - death,
 - first invasive mechanical ventilation use, and
 - first admission to ICU

will be analyzed according to survival analysis methodology detailed in section 4.1 with the following modifications:

- the common representation of survival curves using the Kaplan-Meier estimator will be replaced by the cumulative incidence function,
- the presence of other competing event(s) is/are treated as censored.
- The comparison between treatment and control will be performed in the PP population instead of FAS as described in section 7.1.2, to assess the robustness of trial results versus the adherence to protocol.

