8.1 Adverse events

Any AE which starts at or after the first administration of study treatment will be considered a Treatment Emergent Adverse Event (TEAE). Pre-treatment AEs and TEAEs will be presented separately. Pre-treatment AEs will be presented in the listings only. In case of missing or incomplete dates not allowing a direct allocation to any of the two categories of AEs, a worst-case allocation will be done according to the available parts of the onset and the end dates (see Table 8). The AE will be allocated to the first category allowed by the available data, according to the following order:

- TEAE;
- Pre-treatment AE.

All AEs will be assigned to a PT and will be classified by primary SOC according to the MedDRA thesaurus. In addition, each AE will be graded according to severity definitions as “Mild”, “Moderate” or “Severe”.

TEAEs will be reported on a per-subject basis, i.e. if a subject reported the same event repeatedly (i.e. events mapped to the PT) the event will be counted only once.

For summaries, the drug-event relationship will be assessed as “None”, “Unlikely”, “Possible” “Probable” or “Highly probable”. Any TEAE reported in the study having a possible, probable or highly probable relationship to IMP will be defined as “Adverse Drug Reaction” (ADR).

The following tables and listings will be presented by treatment group:

- An overview of TEAEs including the number of subjects who exhibited at least one TEAE, at least one severe TEAE, at least one serious TEAE, at least one non-serious TEAE, at least one ADR, at least one serious ADR, number of TEAEs, number of non-serious TEAEs, number of TESAEs, number of ADRs, number of serious ADRs, number of deaths, number of subjects who temporarily interrupted IMP due to a TEAE, number of subjects who permanently interrupted IMP due to a TEAE;
- Summary of TEAEs by primary SOC and PT;
- Summary of TEAEs by primary SOC, PT and Severity;
- Summary of Serious TEAEs by Primary SOC and PT;
- Summary of ADRs by Primary SOC and PT;
- Summary of ADRs by Primary SOC and PT and Severity;
- Summary of TEAEs leading to IMP temporary interruption by Primary SOC and PT;
- Summary of TEAEs leading to IMP permanently interruption by Primary SOC and PT;
- Summary of TEAEs leading to Death by Primary SOC and PT;
- Listing of all AEs by Subject;
- Listing of SAEs by Subject;
- Listing of ADR by Subject;
- Listing of Deaths.

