Time to supplemental oxygen requirement (days)	Time to supplemental oxygen requirement (days) = First Administration start date - Date of randomization
Time to mechanical invasive ventilation use (days)	Time to (invasive) mechanical ventilation use (days) = First (invasive) Mechanical Ventilation start date - Date of randomization
Time to admission to ICU (days)	Time to admission to ICU (days) = Admission date - Date of randomization
Time to rescue medication (days)	Time to rescue medication (days) = First rescue treatment start date - Date of randomization
Overall survival (days)	Overall survival (days) = Date of death - Date of randomization
Subject with improvement based on Likert scale	Improvement = any of these answers: 
 • 1 = minimally better, • 2 = moderately better, and • 3 = markedly better
Cumulative quantity (L) of oxygen treatment	Cumulative quantity of oxygen treatment (L) = Sum of all Quantity (L) in CONCOMITANT OXYGEN TREATMENT form, from randomization to time point of interest. It is defined as supplemental oxygen requirement any increased used of oxygen compared to baseline.
Cumulative duration (hours) of oxygen treatment	Cumulative duration of oxygen treatment (hours) = Sum of duration of oxygen administration (hours) in CONCOMITANT OXYGEN TREATMENT form, from randomization to time point of interest. Duration of oxygen administration (hours) = Administration end date/time - Administration start date/time / 60
Cumulative duration (hours) of mechanical ventilation	Cumulative duration of mechanical ventilation (hours) = Sum of duration of mechanical ventilation (hours) in MECHANICAL VENTILATION form, from randomization to time point of interest. Duration of mechanical ventilation (hours) = End date/time - Start date/time / 60
Duration (days) of ICU stay	Duration of ICU stay (days) = Discharge date - Admission date
Change from baseline	For changes from baseline the baseline value will constitute the minuend and the later value the subtrahend.
Conversion of Time Intervals	If a time interval was calculated in minutes, hours or days and needs to be converted into months or years the following conversion factors will be used: 
 • 1 hour = 60 minutes • 1 day = 24 hours • 1 week = 7 days • 1 month = 30.4375 days • 1 year = 365.25 days

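### On its natural reading, the phase 3 death component in SAP 7.1.3.2 stops at ICU admission or invasive ventilation and misses later deaths, and no other planned time-to-event analysis looks at death alone

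*SAP*

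**What the plan says.** For phase 3, SAP 7.1.3.2 states: "Time to event for each single component of the severe primary endpoint will be performed separately". The events listed are death, first invasive mechanical ventilation and first ICU admission. The methods are those of SAP 4.1, where "Comparison of curves among arms will be performed with the log-rank test", with two modifications:

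- The first changes what is plotted: "the common representation of survival curves using the Kaplan-Meier estimator will be replaced by the cumulative incidence function".
- The second sets a rule for events other than the one being analysed: "the presence of other competing event(s) is/are treated as censored".

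SAP 7.1.3.1 applies the same two lines to the phase 2 components: supplemental oxygen, mechanical ventilation, ICU admission and rescue medication. Death is not in that list.

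The SAP does not define which events compete with which component. It names no estimator for the cumulative incidence function, and it does not say whether the censoring line applies to the curve, the test or both.

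Death appears in other places. Table 7 (SAP 9.1) has the row "Overall survival (days) = Date of death - Date of randomization", but no part of section 7 uses it. The safety outputs include a "Summary of TEAEs leading to Death by Primary SOC and PT", a count of deaths and a listing. The phase 3 composite counts death.

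**The concern.** A competing event is one that prevents the event of interest. Death prevents later ICU admission or ventilation; ICU admission and ventilation do not prevent death. If they censor the death analysis, a patient admitted to ICU on day 3 who dies on day 10 leaves that analysis on day 3, recorded as alive. Patients who reach ICU or a ventilator have a worse prognosis than those who do not, so the censoring is informative.

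A treatment that delays ICU admission without changing later mortality, or while worsening it, could not be recognised from such an analysis. The phase 3 composite cannot show it either, because it stops at the first event.

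In phase 2 the rule has the matching fault: events that do not end follow-up censor one another, while the one event that precludes all the others is not named.

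**Working it through.** **1. The plan's own event count.** Inputs: 111 patients, 2:1 allocation (74 reparixin, 37 control), exponential times, 21 days of follow-up (SAP 3.2), no drop-out (Protocol 9.1), and the effect in Protocol 9.1: "expecting to double the median time freedom from severe composite event using Reparixin compared to control (from 2-4 to 4-8 days". Expected composite events by day 21 = 37 × (1 − 0.5^(21/m_C)) + 74 × (1 − 0.5^(21/m_R)), where m_C and m_R are the control and reparixin medians.

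- Medians 2 and 4 days: 36.97 + 72.06 = 109.0. This reproduces the stated 109 events, which is 109/111 = 98% of patients.
- Medians 4 and 8 days: 36.03 + 62.00 = 98.0, or 98/111 = 88%.

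If a first composite event ends observation for the death component, only about 2% to 12% of patients reach day 21 without being censored at another component or dying.

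**2. Deaths not counted.** Two inputs are needed that the documents do not give, so both are assumptions: q, the share of composite events in which death comes first (5% to 20%), and d, the share of the remaining patients with an event who die later (20% to 40%). With n = 109 events:

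- deaths counted = q × n
- deaths not counted = d × (1 − q) × n
- share not counted = d(1 − q) / [q + d(1 − q)]

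| q | d | counted | not counted | share not counted |
|---|---|---|---|---|
| 5% | 20% | 5.5 | 20.7 | 79% |
| 5% | 40% | 5.5 | 41.4 | 88% |
| 10% | 20% | 10.9 | 19.6 | 64% |
| 10% | 40% | 10.9 | 39.3 | 78% |
| 20% | 20% | 21.8 | 17.4 | 44% |
| 20% | 40% | 21.8 | 34.9 | 62% |

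The share does not depend on n, so medians of 4 and 8 days give the same percentages. The loss is also the same whichever curve is drawn: an Aalen-Johansen estimate with the other components as competing events counts death only as a first event.

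**3. What the unclear censoring line does to the curve.** Assume constant cause-specific hazards and q = 10%, with λ = ln 2 / median. The Aalen-Johansen value at day 21 is q(1 − e^(−21λ)). If the curve itself censors competing events, it is 1 − e^(−21qλ), that is, 1 minus Kaplan-Meier.

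| medians, control / reparixin | Aalen-Johansen | 1 − Kaplan-Meier |
|---|---|---|
| 2 / 4 days | 10.0% / 9.7% | 51.7% / 30.5% |
| 4 / 8 days | 9.7% / 8.4% | 30.5% / 16.6% |

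A simulation of the 4-day median case gave 9.7% and 30.5%, in agreement. With medians of 2 and 4 days, the difference between arms is 0.3 percentage points on one reading (10.0 − 9.7) and 21.2 on the other (51.7 − 30.5). The choice therefore has to be written down.

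**4. Other planned analyses.** SAP 7.2.2.6 and 7.2.2.7 compare the proportions ventilated and admitted to ICU between arms, without mention of censoring at other components. There is no matching comparison for death. The component rates in SAP 7.1.2 carry the note "only the first event will be considered", which may restrict death to first events there too.

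**The case against.** A reader might infer that the two modifications contradict each other and that the cumulative incidence is in fact 1 minus Kaplan-Meier. The text does not establish this. SAP 4.1 supplies both a curve and a test. The first modification replaces the curve, and the second can be read as governing the test. A cumulative incidence curve beside a cause-specific log-rank test that censors competing events is a standard, coherent pairing. What stands is an ambiguity, and the 1 − Kaplan-Meier column above applies only if the censoring line also governs the curve.

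The SAP never says outright that the other components are the competing events, and Table 7 derives each time from randomization without cutting it at another component. That is fair, but the bulleted components are the only events named, and a programmer would have nothing else to censor on.

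Death is also covered elsewhere: in the phase 3 composite, in the phase 2 sensitivity composite that adds death, as the worst category of the clinical severity score, and in the safety outputs. All of this is true. However, the composites stop at the first event, and neither the score nor the safety outputs give a time-to-event comparison of death between arms.

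Finally, these are sensitivity analyses. The decision to go on to phase 3 rests on the primary analysis alone, and SAP 4.7 foresees a protocol amendment and an updated SAP before phase 3. This lowers the severity. It does not remove the point, because SAP 7.1.3.1 lets sensitivity results shape the phase 3 adaptations.

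**Conclusion.** The concern holds for the component analyses of SAP 7.1.3. On the natural reading, the phase 3 death component does not count deaths after ICU admission or invasive ventilation, the censoring is informative, and no other planned between-arm time-to-event analysis addresses death alone. The phase 2 text has the same fault, with death left out.

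The plan's own assumptions put 88% to 98% of patients at a first composite event by day 21, so the loss could be large. The 44% to 88% range rests on the assumed q and d. A reader might infer that most deaths are certain to be lost, or that the ventilation component would be close to empty. The documents support neither: the lower end of the range is below one half, and the order in which components occur is not given.

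The primary log-rank tests, the ventilation and ICU incidence comparisons and the safety death outputs are unaffected. Severity: should be fixed.

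**What to change.** - **Death.** Take death out of the phase 3 component list in SAP 7.1.3.2. Add an analysis of all-cause death from randomization by Kaplan-Meier and log-rank, using the existing overall survival row of Table 7, with no censoring at ICU admission or ventilation.
- **Non-fatal components, both phases.** Replace the second modification in SAP 7.1.3.1 and 7.1.3.2 with: only death is a competing event; the other non-fatal components do not end follow-up; cumulative incidence is estimated by the Aalen-Johansen method; arms are compared by a cause-specific log-rank test. In that test, death is the only competing event that censors.

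The cost is SAP wording and programming. The dates of death, ICU admission, ventilation and rescue medication are already used in Table 7, so no new data are needed.

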7.2 Analysis of secondary efficacy endpoints

7.2.1 Descriptive Analysis

Descriptive in nature analyses will be performed on all secondary endpoints (section 3.5.2) at each available time points by means of descriptive statistics (section 4.1).

In case of continuous measures, analyses will be provided for:

- baseline visit,
- each post-baseline visit, and
- the change from baseline measurements to each visit.

In case of categorical variables, shift tables showing difference as to the respective classifications at baseline might be provided.

7.2.2 Comparison between treatments

Along with the above summary statistics, comparisons between treatments will be performed as detailed in the next sub-sections. Parametric test (i.e. two-sample t-test for continuous variables, Chi-square test for categorical) will be adopted as first choice. In case the required assumptions are not met, the corresponding non-parametric counterpart will be used (i.e. the two-sample Mann–Whitney U test for continuous variables, and the Fisher’s Exact test for the categorical). Normality of continuous data is assessed by Kolmogorov-Smirnov test.

Comparison will be performed at each available time point, where applicable. Any exception will be declared.

7.2.2.1 *Composite endpoint of phase 2 using Oxygen Delivery System Classification*

The composite endpoints will be summarized along with their single component by a binomial response rate at each time point (only the first event will be considered). The Clopper-Pearson method will be used to estimate the two-sided 95% CIs.

Time to composite endpoint(s) will be performed using the KM methodology and the one-sided log-rank test will be used to test for differences between treatment groups.

7.2.2.2 *Changes in clinical severity score*

Number and proportion along with the 95% confidence interval (Clopper-Pearson’s formula) of subjects with a clinical severity score improvement of at least two points compared to randomization or live discharge from the hospital will be calculated and compared.

7.2.2.3 *Dyspnea severity (Liker scale and VAS scale)*

The comparison of the Liker scale between the two study treatment arms will be performed by means of Wilcoxon signed-rank test, given its ordinal nature.

Number and proportion along with the 95% confidence interval (Clopper-Pearson’s formula) of subjects with

any improvement (improved vs not-improved) will be calculated and compared.

VAS scale comparison between treatments will be performed according to its continuous nature.

7.2.2.4 *Changes in body temperature*

Comparison between treatments in change from baseline of the body temperature will be performed according to the continuous nature of the variable.

7.2.2.5 *Incidence of supplemental oxygen treatment*

Number and proportion along with the 95% confidence interval (Clopper-Pearson's formula) of subjects who worsened according to PaO₂/FiO₂ and to Oxygen Delivery System Classification based on oxygen support will be calculated and compared.

At each time point the number and proportion of patients within each class (Severe, Moderate, or Mild for PaO₂/FiO₂; Invasive, High Flow, or Low Flow for the type of support) will be provided.

Finally, summary of cumulative quantity (L) and cumulative duration (hours) of oxygen treatment will be performed at 7 days and subsequent time points considering the variable as continuous.

7.2.2.6 *Incidence and duration of mechanical ventilation use*

Number and proportion along with the 95% confidence interval (Clopper-Pearson's formula) of subjects requiring mechanical ventilation will be calculated and compared.

Comparison between treatments in cumulative duration (hours) of mechanical ventilation will be performed at 7 days and subsequent time points considering the variable as continuous. Analysis will be performed overall and stratified by Invasive/Non-invasive mechanical ventilation.

7.2.2.7 *Incidence of ICU admission need*

Number and proportion along with the 95% confidence interval (Clopper-Pearson's formula) of subjects requiring ICU admission will be calculated and compared.

Comparison between treatments in duration (days) of ICU stay will be performed considering the variable as continuous.

7.2.2.8 *Change from baseline in lung damage extension and lung exudation degree (assessed by Chest CT or Rx)*

The comparison of the clinical evaluation of lung damage extension and lung exudation between the two study treatment arms will be performed by means of Wilcoxon signed-rank test.

7.2.2.9 *Respiratory parameters*

Change from baseline of FiO₂, Respiration rate, PaO₂, SpO₂ and PaO₂/FiO₂ will be compared between treatments considering the continuous nature of these variables.

7.2.2.10 *CRP and Hs-CRP*

CRP (mg/L) and Hs-CRP (mg/L) will be compared between treatments considering their continuous nature.

7.3 **Analysis of exploratory efficacy endpoints**

Explorative endpoints (section 3.5.3) will be analyzed at each available time points by means of descriptive statistics. Specifically, analyses will be provided for baseline visit, each post-baseline visit, and the change from baseline measurements to each visit. Comparison between treatments will be performed by means of two-sample t-test or, if assumptions of normality is not confirmed (by Kolmogorov-Smirnov test), two-sample Mann-Whitney U test.

In case of different units of measure considered for the same laboratory parameter, all values will be converted

into Standard International (SI) units (if applicable) or to the same unit.

8. Evaluation of Safety

